6.1.2 Procedures for handling subjects incorrectly enrolled patients

Procedures for withdrawal of incorrectly enrolled patients are presented in Section 4.3

6.2. Dosage and Administration

The treatment to be used in the run in phase of this trial for patients > 30kg is outlined in the Table below:

Drugs	Dose/Potency	Dose Frequency	Route of Administration	Regimen/Treatment Period
1. Durvalumab	1500 mg	Q4 weeks	IV infusion	Maximum of 13 doses
2. Tremelimumab	75mg	Q4 weeks	IV infusion	Maximum of 4 doses

If 2 or more DLTs (defined in Section 6.4) are observed in the run-in phase, the following treatment will be used for the remaining 14 patients to be treated on the clinical trial protocol:

Drugs	Dose/Potency	Dose Frequency	Route of Administration	Regimen/Treatment Period
1. Durvalumab	1500 mg	Q6 weeks	IV infusion	Maximum of 9 doses
2. Tremelimumab	75mg	Q6 weeks	IV infusion	Maximum of 3 doses

Patients who experience a DLT in the run in phase, will have dose interruptions/modifications as outlined in Appendix 1.

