19. Has a known history of Human Immunodeficiency Virus (HIV) (HIV 1/2 antibodies).
20. Has evidence of acute or chronic hepatitis B, or hepatitis C
21. Has received a live vaccine within 30 days prior to the first dose of trial treatment.
22. Has a Mean QT interval corrected for heart rate (QTc) ≥ 470 ms calculated from 3 electrocardiograms (ECGs) using Fredericia's Correction
23. Has a history of primary immunodeficiency or an allogeneic organ transplant
24. Has a history of hypersensitivity to durvalumab or tremelimumab excipient
25. Known history of previous clinical diagnosis of tuberculosis
26. Uncontrolled intercurrent illness including, but not limited to symptomatic congestive heart failure, uncontrolled hypertension, unstable angina pectoris, cardiac arrhythmia, active peptic ulcer disease or gastritis, seizures

Investigational Product(s), Dose, and Mode of Administration:

Durvalumab, 1500 mg Q4W (equivalent to 20 mg/kg Q4W) via IV infusion for up to 13 doses (fixed dose for patients > 30kg)

Tremelimumab 75 mg Q4W (equivalent to 1 mg/kg Q4W) via IV infusion for up to 4 doses (fixed dose for patients > 30kg)

Study Assessments and Criteria for Evaluation:

Safety Assessments:

Patients enrolled in the study will be evaluated by the investigator/co-investigator prior to each dose of durvalumab and tremelimumab (more frequently if clinically indicated), and assessed for adverse events. All adverse events will be graded via CTCAE v. 4.

Efficacy Assessments:

RECIST criteria 1.1 will be used to evaluate treatment responses in all patients enrolled on the study. Patients will have baseline imaging obtained within 4 weeks of starting the investigational agents. Repeat imaging will be performed every 8 weeks (+/- 1 week).

Pharmacodynamic / Pharmacokinetic Assessments (if applicable):

None

Statistical Methods and Data Analysis:

The primary objective of this study is to evaluate the safety and tolerability of durvalumab and tremelimumab with hypofractionated radiation therapy in patients with recurrent head and neck cancer who have previously received immunotherapy. The total sample size for this evaluation is 20 patients evaluated in a dose de-escalation design. Initially, durvalumab dosing will be 1500 mg IV Q4weeks and tremelimumab dosing will be 75mg IV Q4W.

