Both durvalumab and tremelimumab have well established toxicity profiles as a single agent and in combination. However, the combination of durvalumab tremelimumab and palliative radiation has not been previously studied, this study will include a formal safety analysis in the first 6 patients accrued. Enrollment will be halted until these first 6 patients complete the first two cycles of treatment (8 weeks), and are evaluable for acute toxicities (toxicities reported within the 1st 8 weeks after treatment initiation). Specifically, if 2 or more DLTs (Refer to Section 6.4) are observed, then, durvalumab dosing will be modified to 1500 mg IV Q6 weeks x 9 doses and tremelimumab 75mg IV Q6 weeks x 3 doses for the remaining 14 patients (fixed dosing for patients > 30kg). If 1 or fewer DLTs are observed, then an additional 14 patients will be enrolled and treated at the initial dose and schedule of durvalumab and tremelimumab. Patients in the run in phase who experience DLTs will undergo dose modifications described in Appendix 1.

Toxicities will be graded based on CTCAE v. 4 and summarized as the number and percentage of patients with each type of toxicity. Responses will be summarized as frequencies and percentages. The Kaplan Meier method will be used to estimate overall survival and progression free survival. Outcomes will be calculated from the date of study entry to the date of the corresponding event.

We will use multivariate statistics to test the hypotheses that pretreatment intratumoral immune cell phenotype and PD-L1 expression predict response to therapy, and that therapy alters systemic immunophenotype.

Sample Size Determination:

There are multiple ongoing studies in various tumor types exploring the activity of durvalumab and tremelimumab. In a published report of the combination in patients with advanced NSCLC treated on a phase Ib study, Grade 3-4 toxicity was observed in 17% of patients. Similarly, in single institution reports of SBRT with the monoclonal antibody, grade 3 or higher toxicity was reported in 6-16% of patients. With a 20 patient accrual goal, toxicity rates can be estimated to within 22% with 95% confidence. Any toxicity with at least 10% prevalence has at least an 87% chance of being observed. This design allows us to reasonably exclude a clinically significant increase in toxicity with the addition of radiation therapy to the durvalumab and tremelimumab combination as defined by the upper bound of the confidence interval.

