3.3 Study Oversight for Safety Evaluation

The primary endpoint of this study is safety and tolerability. Durvalumab and tremelimumab will be given at the recommended fixed dosing in patients > 30kg (see section 1.3.1), which has been shown to result in minimal toxicity, but encouraging efficacy in NSCLC patients. Since the concurrent administration of radiation therapy is previously unstudied in this cohort, the first 6 patients will represent a run-in phase, and enrollment will be halted until all patients complete

the first two cycles of treatment (8weeks) These 6 patients will be assessed for DLTs and will determine if a modified dosing schedule of durvalumab and tremelimumab will be applied in the expansion phase.

In keeping with the study primary endpoint, a stopping rule will be implemented in the unlikely event that the combination under study is deemed to have unacceptably high toxicities. Enrollment will be halted if more than 3 patients experience a Grade 4 or higher drug related toxicity (CTCAE v. 4) during the trial or up to 30 days after the last investigational drug infusion. The likelihood of observing 3 or more Grade 4+ drug-related DLTs is 80% if the true rate is 20% and the likelihood is 91% if the true rate is 25%. This rule has an 83% chance of stopping in the 1st 10 patients if the true rate is 40%. Section 10.2.2 provides some guidelines on the attribution of toxicity to the drug and radiation combination. The study will be reviewed by the University of Washington/Fred Hutchinson Cancer Research Center Data Safety and monitoring board.

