6.4 Definition of DLT

Dose-limiting toxicities (DLTs) will be evaluated during the run in phase consisting of the first 6 patients enrolled in this trial. The period for evaluating DLTs will be from the time of first administration of durvalumab or tremelimumab until 28 days (cycle 1). Adverse event monitoring will continue for these subjects throughout the course of their treatment (beyond cycle 1) as outlined in the Schedule of Study Assessments, these adverse events will include potential XRT related toxicities. Subjects who do not remain on the study up to this time for reasons other than DLT will be replaced with another subject. Grading of DLTs will follow the guidelines provided in the Common Terminology Criteria for Adverse Events (CTCAE) version 4.0.

A DLT will be defined as any Grade 3 or higher toxicity that occurs during the DLT evaluation period. Toxicity that is clearly and directly related to the primary disease or to another etiology is excluded from this definition. The following will be DLTs:

- Any Grade 4 irAE
- Any \geq Grade 3 colitis
- Any Grade 3 or 4 noninfectious pneumonitis irrespective of duration
- Any Grade 2 pneumonitis that does not resolve to \leq Grade 1 within 3 days of the initiation of maximal supportive care
- Any Grade 3 irAE, excluding colitis or pneumonitis, that does not downgrade to Grade 2 within 3 days after onset of the event despite optimal medical management including systemic corticosteroids or does not downgrade to \leq Grade 1 or baseline within 14 days
- Liver transaminase elevation $> 8 \times$ ULN or total bilirubin $> 5 \times$ ULN
- Any \geq Grade 3 non-irAE, except for the exclusions listed below
 - Grade 3 fatigue lasting \leq 7 days
 - Grade 3 endocrine disorder (thyroid, pituitary, and/or adrenal insufficiency) that is managed with or without systemic corticosteroid therapy and/or hormone replacement therapy and the subject is asymptomatic
 - Grade 3 inflammatory reaction attributed to a local antitumor response (eg, inflammatory reaction at sites of metastatic disease, lymph nodes, etc)
 - Concurrent vitiligo or alopecia of any AE grade
 - Grade 3 infusion-related reaction (first occurrence and in the absence of steroid prophylaxis) that resolves within 6 hours with appropriate clinical management

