 - Grade 3 or 4 neutropenia that is not associated with fever or systemic infection that improves by at least 1 grade within 3 days. Grade 3 or Grade 4 febrile neutropenia will be a DLT regardless of duration or reversibility

- Grade 3 or 4 lymphopenia
- Grade 3 thrombocytopenia that is not associated with clinically significant bleeding that requires medical intervention, and improves by at least 1 grade within 3 days
- Isolated Grade 3 electrolyte abnormalities that are not associated with clinical signs or symptoms and are reversed with appropriate maximal medical intervention within 3 days
- Prolonged delay (>2 weeks) in initiating cycle 2 due to treatment-related toxicity
- Grade 5 toxicity, i.e. death

Dose modification/delays according to Section 6.5.1 and Appendix 1 will apply to the patients who experience DLTs in the run in phase.

Immune-related AEs are defined as AEs of an immune nature (ie, inflammatory) in the absence of a clear alternative etiology. In the absence of a clinically significant abnormality, repeat laboratory testing will be conducted to confirm significant laboratory findings prior to designation as a DLT.

6. 5 Dose Modification and Toxicity Management

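### If the run-in fails without the pooled Grade 4+ halt, the other 14 patients get Q6W at the same dose per infusion, with no DLT criterion or decision point for that schedule

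*Combined protocol and SAP*

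**What the plan says.** The Synopsis (Statistical Methods and Data Analysis) describes 20 patients "evaluated in a dose de-escalation design". Treatment starts every 4 weeks with durvalumab 1500 mg (up to 13 doses) and tremelimumab 75 mg (up to 4). Radiotherapy begins two weeks after the first dose.

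Section 6.2 sets the fallback. With 2 or more DLTs in the run-in, "the following treatment will be used for the remaining 14 patients to be treated on the clinical trial protocol". That treatment is the same 1500 mg and 75 mg per infusion every 6 weeks, up to 9 and 3 doses.

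Section 6.4 limits the DLT assessment: "Dose-limiting toxicities (DLTs) will be evaluated during the run in phase consisting of the first 6 patients enrolled in this trial". It sets the window at 28 days from first administration. It also provides that "Subjects who do not remain on the study up to this time for reasons other than DLT will be replaced with another subject", and its list contains "Prolonged delay (>2 weeks) in initiating cycle 2 due to treatment-related toxicity".

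The Synopsis and Section 3.3 use a longer period. Enrolment stops until the first 6 patients have completed two cycles, or 8 weeks, and the DLT decision is tied to that review. It is the only planned pause, and Section 11.2.4 plans no interim analysis.

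Section 3.3 adds a rule for the whole trial: "Enrollment will be halted if more than 3 patients experience a Grade 4 or higher drug related toxicity". It covers both schedules and runs to 30 days after the last infusion.

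**The concern.** Safety is the primary endpoint, and the run-in exists to decide whether the starting schedule is acceptable. If it is not, the plan moves all 14 remaining patients to another schedule and states no DLT result that would make that schedule unacceptable. Many DLTs fall below Grade 4: Grade 3 colitis, Grade 3 pneumonitis, Grade 2 pneumonitis that does not resolve, and most Grade 3 events that are not immune-related. The pooled rule does not count them. Safety data on Q6W would be collected, but below Grade 4 no prespecified decision depends on them. All 14 patients could be enrolled while Grade 3 DLTs ran at a rate that led the plan to act in the first 6.

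**Working it through.** **Inputs from the documents.** Run-in limit: 2 or more of 6 (Synopsis, Section 6.2). Patients remaining: 14 of at most 20 (Sections 3.1, 6.2). Both schedules: Section 6.2. DLT window: 28 days (Section 6.4), against an 8-week assessment (Synopsis, Section 3.3). Pooled halt: more than 3 patients (Section 3.3).

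**Assumed.** True DLT rates of 10-40%. The 17% in Section 11.3 is a Grade 3-4 toxicity rate for the drug pair, not a DLT rate for the triplet. Patients are taken as independent, with one DLT status each.

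**1. The plan's own figures.** Section 3.3 gives 80%, 91% and 83% for its pooled rule. Binomial P(X≥3) is 79.4% (n=20, rate 20%), 90.9% (n=20, 25%) and 83.3% (n=10, 40%), so they reproduce for 3 or more. For more than 3, as the rule is worded, P(X≥4) is 58.9%, 77.5% and 61.8%. That mismatch is a separate matter; the rule is used below as worded. No figure is given for the run-in limit or for Q6W.

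**2. Planned exposure.**

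| | Q4W | Q6W |
|---|---|---|
| Infusions of each drug by day 28 | 1 | 1 |
| Day of dose 2 | 29 | 43 |
| Infusions of each drug within 8 weeks (56 days) | 2 | 2 |
| Durvalumab per week | 1500/4 = 375 mg | 1500/6 = 250 mg |
| Planned maximum durvalumab | 13 × 1500 = 19,500 mg | 9 × 1500 = 13,500 mg |
| Planned maximum tremelimumab | 4 × 75 = 300 mg | 3 × 75 = 225 mg |

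To day 28 the schedules are identical, radiotherapy included. Over 8 weeks the number of infusions is equal but the second comes two weeks later on Q6W. Dose rate falls by one third.

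**3. Run-in limit and a second check.** With true rate p, the run-in limit is reached with probability a = 1 − (1−p)^6 − 6p(1−p)^5. At p = 0.20, a = 1 − 0.262 − 0.393 = 0.345 (0.3446 before rounding). Suppose the same limit were applied to the first 6 Q6W patients:

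- Equal risk on Q6W: both limits are reached with probability a². If the board then stops, the expected number of patients per trial spared a DLT among the last 8 is a² × 8p.
- Risk lower by one third, in line with dose rate: q = 2p/3, b is the same formula at q, and the results are a × b and a × b × 8q.

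| True run-in DLT rate p | 10% | 17% | 20% | 30% | 40% |
|---|---|---|---|---|---|
| Run-in limit reached | 11% | 27% | 34% | 58% | 77% |
| Both reached, equal risk | 1% | 7% | 12% | 34% | 59% |
| Both reached, risk lower by a third | 1% | 4% | 6% | 20% | 39% |
| Patients spared, equal risk | 0.01 | 0.10 | 0.19 | 0.81 | 1.88 |
| Patients spared, risk lower by a third | 0.00 | 0.03 | 0.07 | 0.32 | 0.83 |

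Example at 30%: a = 0.580, a² = 0.336, and 0.336 × 2.4 = 0.81. With q = 0.20, b = 0.345, a × b = 0.200, and 0.200 × 1.6 = 0.32.

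**4. Overlap with the pooled rule.** Assume equal risk and that half of DLT patients have drug-related Grade 4+ events, and ignore events outside the DLT window. The probability of 2 or more DLTs in each group of 6 with no more than 3 Grade 4+ patients among the 12 (multinomial) is then about 1/6/10/26/41%. Patients spared become 0.01/0.09/0.16/0.63/1.30. At assumed Grade 4+ rates of 5% and 10%, the pooled rule fires over 20 patients with probability 0.016 and 0.133.

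**5. What a stop would cost.** The trial would end with 12 patients. The worst-case 95% half-width is 1.96 × √(0.25/n): 22 points at n=20, as Section 11.3 states, and 28 at n=12. The chance of seeing a 10% toxicity is 1 − 0.9^n: 88% at n=20 (Section 11.3 says at least 87%) and 72% at n=12.

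**The case against.** The strongest objection concerns the window. It is tempting to say that Q6W cannot affect the toxicity that triggered it, because exposure changes only after the DLT window closes. That holds for the 28 days in Section 6.4. The Synopsis and Section 3.3 tie the decision to 8 weeks, and the cycle-2 delay item cannot be established within 28 days. On the 8-week reading the second dose moves inside the decision period. The documents do not reconcile the two, so equal DLT risk is only one assumption. This objection stands, which is why the table carries a lower-risk row.

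A reader might also infer that Q6W patients would have no stopping protection. The documents do not support that. The pooled Grade 4+ rule carries run-in events forward, so 4 or more such patients in the run-in halt enrolment and Q6W does not start. There is monitoring board review (Sections 3.3, 13.2.1), weekly adverse event review (Section 14), early termination for safety concerns (Section 13.3) and individual discontinuation (Appendix 1). Step 4 understates the pooled rule, because that rule also counts events outside the DLT window. None of these controls, however, states a Grade 3 DLT result or a review time for Q6W, and individual discontinuation does not protect the next patient enrolled.

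Lengthening the interval is also a defensible choice. The Synopsis describes the pair's toxicity as well established, and Section 1.3.1 chose the equivalent tremelimumab dose to limit toxicity. That supports trying Q6W; it does not supply a criterion for judging it.

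**Conclusion.** The gap is real but conditional. It opens only if the run-in limit is reached and the pooled halt has not been triggered. The plan then has no prespecified response to DLTs below Grade 4 on its own fallback schedule.

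The size depends on the unknown DLT rate and on how far Q6W lowers it. At true rates of 20% or less, a second check spares at most about 0.2 patients per trial under equal risk and under 0.1 if risk falls by a third. At 30-40% it spares 0.81-1.88 or 0.32-0.83. These counts assume that the board always stops and, outside step 4, leave out the pooled halt. The benefit is material mainly at 30% or more, a range the documents neither support nor exclude. This is a modest, conditional improvement, worth making because it bears on the primary endpoint and needs little more than wording. It does not show that Q6W is unsafe or that the de-escalation is ineffective.

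**What to change.** In Sections 6.2 and 6.4, for use only if the run-in fails:

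- Apply the existing DLT definition and the 2-of-6 limit to the first 6 evaluable Q6W patients. Fill non-evaluable places (Sections 4.4 and 6.4) from within the 14, so that the maximum of 20 holds.
- State one DLT window for both cohorts, and bring the Synopsis, Section 3.3 and Section 6.4 into line with it.
- Pause enrolment until the sixth patient has passed the cycle-2 delay limit. On Q6W that is day 43 + 14 = day 57, plus the visit window, so slightly over 8 weeks.
- If the limit is reached, halt and refer to the monitoring board before enrolling the rest.
- Report toxicity by schedule as well as pooled, and state that the check asks whether Q6W is acceptable, not whether it is safer than Q4W.

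The cost is protocol wording and, in this branch only, one further accrual pause. At true Q6W DLT rates of 10-20% the check would flag the schedule with probability 11-34%. An observed 2 of 6 has an exact 95% interval of 4.3-77.7%, so a flag should prompt board review and not be read as an estimate of the rate. Each non-evaluable Q6W patient takes one of the 8 places left after the check. If the board stops, the trial ends with 12 evaluable patients, 6 per schedule, and the loss of precision shown in step 5.

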6.3 Dose Escalation Decision Rules

There will be no dose escalations performed on this study.

6.4 Definition of DLT

Dose-limiting toxicities (DLTs) will be evaluated during the run in phase consisting of the first 6 patients enrolled in this trial. The period for evaluating DLTs will be from the time of first administration of durvalumab or tremelimumab until 28 days (cycle 1). Adverse event monitoring will continue for these subjects throughout the course of their treatment (beyond cycle 1) as outlined in the Schedule of Study Assessments, these adverse events will include potential XRT related toxicities. Subjects who do not remain on the study up to this time for reasons other than DLT will be replaced with another subject. Grading of DLTs will follow the guidelines provided in the Common Terminology Criteria for Adverse Events (CTCAE) version 4.0.

A DLT will be defined as any Grade 3 or higher toxicity that occurs during the DLT evaluation period. Toxicity that is clearly and directly related to the primary disease or to another etiology is excluded from this definition. The following will be DLTs:

- Any Grade 4 irAE
- Any \geq Grade 3 colitis
- Any Grade 3 or 4 noninfectious pneumonitis irrespective of duration
- Any Grade 2 pneumonitis that does not resolve to \leq Grade 1 within 3 days of the initiation of maximal supportive care
- Any Grade 3 irAE, excluding colitis or pneumonitis, that does not downgrade to Grade 2 within 3 days after onset of the event despite optimal medical management including systemic corticosteroids or does not downgrade to \leq Grade 1 or baseline within 14 days
- Liver transaminase elevation $> 8 \times$ ULN or total bilirubin $> 5 \times$ ULN
- Any \geq Grade 3 non-irAE, except for the exclusions listed below
 - Grade 3 fatigue lasting \leq 7 days
 - Grade 3 endocrine disorder (thyroid, pituitary, and/or adrenal insufficiency) that is managed with or without systemic corticosteroid therapy and/or hormone replacement therapy and the subject is asymptomatic
 - Grade 3 inflammatory reaction attributed to a local antitumor response (eg, inflammatory reaction at sites of metastatic disease, lymph nodes, etc)
 - Concurrent vitiligo or alopecia of any AE grade
 - Grade 3 infusion-related reaction (first occurrence and in the absence of steroid prophylaxis) that resolves within 6 hours with appropriate clinical management
 - Grade 3 or 4 neutropenia that is not associated with fever or systemic infection that improves by at least 1 grade within 3 days. Grade 3 or Grade 4 febrile neutropenia will be a DLT regardless of duration or reversibility

- Grade 3 or 4 lymphopenia
- Grade 3 thrombocytopenia that is not associated with clinically significant bleeding that requires medical intervention, and improves by at least 1 grade within 3 days
- Isolated Grade 3 electrolyte abnormalities that are not associated with clinical signs or symptoms and are reversed with appropriate maximal medical intervention within 3 days
- Prolonged delay (>2 weeks) in initiating cycle 2 due to treatment-related toxicity
- Grade 5 toxicity, i.e. death

Dose modification/delays according to Section 6.5.1 and Appendix 1 will apply to the patients who experience DLTs in the run in phase.

Immune-related AEs are defined as AEs of an immune nature (ie, inflammatory) in the absence of a clear alternative etiology. In the absence of a clinically significant abnormality, repeat laboratory testing will be conducted to confirm significant laboratory findings prior to designation as a DLT.

6. 5 Dose Modification and Toxicity Management

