The response rates to dual CTLA and PDL1 blockade and radiation therapy after prior immunotherapy are unknown. If objective responses are demonstrated, or encouraging progression free survival is observed in the 20 patients enrolled on the study, it would merit further investigation in a larger study powered to examine efficacy endpoints.

SCHEDULE OF STUDY ASSESSMENTS

Assessments to be performed at the times stipulated in the table and as clinically required in the management of the subject	Screening	all assessments to be performed pre-infusion unless stated otherwise				
		cycle 1		cycle 2 - 4	cycle 5 -13	
		week 1	week 3	week 1	week 1	end of treatment
Day	- 28 to - 1	Day 1 of the Week				
Week	-4 to -1	(±3 days)			(±7 days)	
Written informed consent	X					
Demography and history of tobacco and alcohol use	X					
Previous treatments for head and neck cancer	X					
Tumor tissue sample (Section 8.3.2)	X					
Formal verification of eligibility criteria	X					
Medical and surgical history	X					

Assessments to be performed at the times stipulated in the table and as clinically required in the management of the subject	Screening	all assessments to be performed pre-infusion unless stated otherwise					
		cycle 1		cycle 2 - 4		cycle 5 - 13	
		week 1	week 3	week 1	week 1	end of treatment	LTFM
Day	- 28 to - 1	Day 1 of the Week					
Week	-4 to -1	(±3 days)		(±7 days)			
Urine hCG or serum βhCG ^b	X						
Physical examination ^c	X	X	X	X	X	X	
Vital signs	X	X	X	X	X	X	
Weight	X	X		X	X		
Electrocardiogram ^d	X						
Durvalumab administration ^e		X		X	X		
Tremelimumab administration ^e		X		X		X	
Adverse event/serious adverse event assessment	X	All Visits					
Radiation therapy evaluation and radiation planning/simulation	X						
Palliative Radiation therapy		XRT to begin 2 weeks after the first dose of Durvalumab and tremelimumab and to be completed in 2 weeks					
ECOG performance status	X	X	X	x	X	X	

Assessments to be performed at the times stipulated in the table and as clinically required in the management of the subject	Screening	all assessments to be performed pre-infusion unless stated otherwise					
		cycle 1		cycle 2 - 4		cycle 5 - 13	
		week 1	week 3	week 1	week 1	end of treatment	LTfM
Day	- 28 to - 1	Day 1 of the Week					
Week	-4 to -1	(±3 days)			(±7 days)		
TSH with reflexive free T4 ^f		X		X ^f	X ^f		
Complete blood count ^g	X	X	X	X	X	X	
Serum chemistry ^g	X	X	X	X	X	X	
Urinalysis ^h	X		X				
Coagulation parameters ⁱ	X	as clinically indicated					

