3.2 Study Schema

The first 6 patients of this study will represent the initial run-in phase of the triplet combination of durvalumab, tremelimumab and HIGRTor SBRT. Fixed doses of Durvalumab and Tremelimumab will be administered on day 1 of therapy. Radiation will be initiated on Week 3 of the 28 day cycle. Radiation will be delivered to a total dose of 24 Gy, given in 3 fractions of 8Gy every other day. Durvalumab will be continued for a total of 13 cycles, and tremelimumab for a total of 4 cycles unless patient withdraws consent, has confirmed disease progression, and/or develops toxicity that results in treatment discontinuation.

Serum correlative studies will be collected at the following timepoints: at baseline, prior to cycle #2, and prior to cycle#4 of treatment. Archived formalin fixed paraffin embedded tissue will be collected from patients enrolled. If the patient does not have archived tissue available, a fresh biopsy will be obtained.

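### The 28-day DLT period ends at about the first scheduled labs after radiation, so a silent post-radiation laboratory DLT may not be placeable inside it, and the 28-day period conflicts with the 8-week evaluation stated elsewhere

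*Combined protocol and SAP*

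**What the plan says.** **DLT period.** Section 6.4 states: "The period for evaluating DLTs will be from the time of first administration of durvalumab or tremelimumab until 28 days (cycle 1"). It counts by occurrence: "A DLT will be defined as any Grade 3 or higher toxicity that occurs during the DLT evaluation period". Among the listed DLTs is "Liver transaminase elevation" above 8 × ULN, or total bilirubin above 5 × ULN. A delay of more than two weeks in starting cycle 2 because of treatment-related toxicity is also listed.

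**Purpose and use.** Section 3.3 explains the run-in: "Since the concurrent administration of radiation therapy is previously unstudied in this cohort, the first 6 patients will represent a run-in phase". Two or more DLTs change the schedule for the other 14 patients. Both the synopsis and Section 6.2 send the reader to Section 6.4 for what counts as a DLT.

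**Radiation.** The Schedule of Study Assessments has "XRT to begin 2 weeks after the first dose of Durvalumab and tremelimumab and to be completed in 2 weeks". Section 3.2 adds: "Radiation will be delivered to a total dose of 24 Gy, given in 3 fractions of 8Gy every other day".

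**Scheduled checks.** In the same schedule, the rows "Physical examination ^c" and "Complete blood count ^g", and the serum chemistry row, are marked at cycle 1 week 1, at cycle 1 week 3, and next at week 1 of cycle 2. Assessments are pre-infusion unless stated otherwise, and safety bloods must be reviewed before an infusion starts.

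**A second period.** The synopsis (Statistical Methods) and Section 3.3 hold enrolment until the six run-in patients have finished two cycles, or 8 weeks. The synopsis ties acute toxicity to those 8 weeks.

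**The concern.** The run-in exists to find out whether adding radiation makes the combination too toxic. Under Section 6.4, only about the second half of the 28 days follows the start of radiation. In that half, the next scheduled examination and blood tests come at a visit that sits on the closing boundary and may lawfully fall after it. A liver abnormality without symptoms is found only by testing. If it is first seen after the boundary, nobody can show that it arose before it.

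The count from six patients sets the schedule for 14 more. Losing even one event can move the result from two DLTs to one.

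**Working it through.** The plan gives no operating characteristics for the 2-of-6 rule, so there is no figure of its own to reproduce on this point. The check is calendar arithmetic, followed by an illustration.

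**Inputs** (elapsed days after the first dose; study day = elapsed + 1)
- DLT period: 28 days (Section 6.4).
- Week 3 visit: 14 ± 3 = 11 to 17.
- Radiation: starts at 14; three fractions every other day = 14, 16, 18.
- Cycle 2 visit: 28 ± 3 = 25 to 31. The table header is broken in the available text and ±7 may apply, giving 21 to 35.
- Competing evaluation: 8 weeks = 56.

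**Step 1: scheduled checks after radiation.** Days 15, 16 and 17, 3 of the 7 permitted week 3 days, fall after a day-14 radiation start. That visit can therefore follow one or two fractions. Its latest day (17) still precedes the third fraction (18). On the nominal radiation timing, nothing is scheduled between the last fraction and cycle 2. The gap between scheduled checks is 28 − 14 = 14 days nominally and 31 − 11 = 20 days at most with ±3.

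**Step 2: cycle 2 visit against the boundary.**

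| Visit window | Permitted days | Beyond 28 elapsed days | If the 28th is also outside |
|---|---|---|---|
| ±3 | 25–31 (7 days) | 29–31: 3/7 = 43% | 28–31: 4/7 = 57% |
| ±7 | 21–35 (15 days) | 29–35: 7/15 = 47% | 28–35: 8/15 = 53% |

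These are shares of permitted calendar days, not of patients or DLTs.

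**Step 3: the other two time limits.** The latest cycle 2 visit (31, or 35 with ±7) is well before 56, so the gap closes if the DLT period is 8 weeks. The delay criterion needs more than 28 + 14 = 42 elapsed days, so it can never be met inside a 28-day period. Section 6.4 therefore does not agree with itself on when the period ends.

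**Step 4: direction of the effect (illustration only).** Let p be an assumed true DLT rate per patient and m an assumed share of DLTs that go uncounted, with q = p(1 − m). Then P(at least 2 of 6) = 1 − (1 − q)^6 − 6q(1 − q)^5. For p = 0.25 and m = 0: 1 − 0.178 − 0.356 = 0.466.

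| p | m = 0 | m = 10% | m = 25% | m = 50% |
|---|---|---|---|---|
| 0.17 | 0.271 | 0.231 | 0.172 | 0.086 |
| 0.25 | 0.466 | 0.406 | 0.314 | 0.167 |
| 0.33 | 0.642 | 0.573 | 0.460 | 0.259 |
| 0.40 | 0.767 | 0.699 | 0.580 | 0.345 |

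The documents supply neither p nor m. The table shows only that uncounted DLTs make the schedule change less likely to trigger.

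**The case against.** - **There is an 8-week evaluation.** On that reading every permitted cycle 2 visit is inside the window and the gap disappears. On either reading the cycle 2 labs exist before the schedule for the other 14 is chosen. This stands as evidence of a contradiction. It does not settle the matter, because the decision rule points to Section 6.4, which says 28 days and treats later events as continued adverse event monitoring.
- **DLTs count by occurrence, not by detection.** Correct. A reader might infer that anything found after 28 days is automatically excluded; the text has no such rule. Because the period is glossed as cycle 1 and labs are pre-infusion, a cycle 2 pre-dose finding could be read as cycle 1 toxicity. That reading is nowhere stated, and without it the onset of a silent event cannot be established.
- **The delay criterion is a backstop.** In part. Under Appendix 1, Grade 3–4 immune hepatitis is treated with steroids tapered over at least 28 days, and dosing resumes only after the taper, so a held case would exceed two weeks. An abnormality that clears sooner escapes. Above 8 × ULN transaminases or 5 × ULN bilirubin, which are the listed liver DLTs, Appendix 1 discontinues drug, and Section 6.4 does not say whether a cycle 2 never started counts as delayed.
- **Few laboratory events are at issue.** Largely right. Neutrophils, platelets and electrolytes appear in Section 6.4 mainly as exclusions, which leaves chiefly the transaminase and bilirubin criteria.
- **Patients are not unobserved.** Also right. Adverse events are assessed at all visits, and extra tests are allowed when clinically indicated. That protects the count of symptomatic events but does not reach silent ones.

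**Conclusion.** The concern holds in a limited form. Under Section 6.4 as written, a silent laboratory DLT arising after radiation may first be seen on or after the 28-day boundary and cannot be dated inside it. The 2-of-6 count may therefore be biased low. This rests on nominal radiation timing, on the 28-day reading, and on no unscheduled test having been done.

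The size of the bias cannot be derived from the documents. Two stronger readings are tempting and unsupported:
- **That about half of post-radiation laboratory DLTs are lost.** The 43% to 57% are shares of permitted visit days. Turning them into missed events would need the distribution of visit days and of onset times, and how many late findings the delay criterion recovers.
- **That nothing is scheduled once radiation starts.** The week 3 visit may follow one or two fractions. Nor do the documents show that silent liver events are what added radiation would mainly produce.

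The wider defect is that the 28-day period, the 8-week evaluation and the delay criterion do not agree on when DLT observation ends. It should be corrected, because the rule rests on six patients and the edit is small.

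**What to change.** Reconcile the synopsis (Statistical Methods), Section 3.3 and Section 6.4, including its delay criterion, so that one stated DLT period feeds the 2-of-6 rule. The choice of period is for the sponsor and investigators.

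If the cycle 1 period is kept, add to Section 6.4:
- that it includes the already scheduled pre-dose cycle 2 examination and labs;
- that abnormalities found there count toward cycle 1;
- how the period closes when cycle 2 is delayed or not started, including whether a cycle 2 that never starts meets the delay criterion.

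If the 8-week period is chosen, Section 6.4 should say so in place of 28 days.

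The cost is a few sentences, with no added visit, sample or patient. With the cycle 1 option the window differs by a few days between patients. The closing rule is what keeps it from running on for weeks when cycle 2 is late.
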